#### G.3.3.1 Medtronic-initiated

- In the case of study termination or suspension for reasons other than a temporary IRB/EC approval lapse, the investigator will promptly inform the IRB/EC.
- In the case of study termination, the investigator must inform the subjects and may inform the personal physician of the subjects to ensure appropriate care and follow-up is provided.
- In the case of a study suspension, subject enrollment must stop until the suspension is lifted by Medtronic. Subjects already enrolled should continue to be followed out of consideration of their safety, rights, and welfare.

#### G.3.3.2 Investigator-initiated

- The investigator will promptly inform:

- Medtronic and provide a detailed written explanation of the termination or suspension.
- The institution (where required per regulatory requirements).
- The IRB/EC.
- The subjects and may inform the personal physicians of the subjects to ensure appropriate care and follow-up is provided.
- In the case of a study suspension:
  - Subject enrollment must stop until the suspension is lifted.
  - Subjects already enrolled should continue to be followed out of consideration of their safety, rights, and welfare.

#### G.3.3.3 IRB/EC-initiated

- The investigator will promptly inform:
  - Medtronic and provide a detailed written explanation of the termination or suspension within 5 business days.
  - The institution (where required per regulatory requirements).
  - The subjects and may inform the personal physicians of the subjects, with the rationale for the study termination or suspension.
- In the case of a study suspension:
  - Subject enrollment must stop until the IRB/EC suspension is lifted.
  - Subjects already enrolled should continue to be followed in accordance with IRB/EC policy or its determination that an overriding safety concern or ethical issue is involved.

#### *G.3.4 Criteria for unblinding*

Reasons for unblinding are:

- All randomized patients will be unblinded during the 6 month follow-up visit. The procedure will be offered to the randomized Control patients that continue to meet eligibility criteria after this visit.
- All randomized patients will immediately be unblinded in case of study termination.
- When a site is terminated, all randomized patients of this site will immediately be unblinded.

Unblinding must be documented including the signature of site study personnel, date and reason for unblinding and must be reported to the Clinical Study Manager. The unblinding will be documented on a separate file that can be found in the ISF.

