All subjects will be followed annually through 36 months post procedure (Table 1), except Crossover subjects. Subjects and blinded study personnel will be unblinded to the randomization assignment at 6 months. Control (sham) subjects may be offered renal denervation therapy (crossover) after their 6-month follow-up visit, according to Section F.10. Crossover subjects will return for office visits at 1, 3, 6, 12 and 24 months post-renal denervation procedure (Table 2).

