#### C.5 Randomization and blinding

Randomization will be stratified by study center at a 1:1 ratio to:

- Denervation group: Subjects remain blinded and are treated with the renal denervation procedure.
- Control group: Subjects remain blinded and remain on the catheterization lab table for at least 20 minutes prior to introducer sheath removal.

Investigational sites will access randomization allocation via a password-protected system that can only be accessed by those approved by the study sponsor.

All study staff and necessary hospital personnel will be instructed that subjects are not to be informed of their randomization assignments and appropriate measures should be taken to minimize the risk of premature unblinding.

The Investigator performing the catheterization lab procedures and his/her designated study staff will be blinded to a subject's randomization group up until the angiography is completed and inclusion/exclusion confirmed. However, investigators performing study follow-up visits

and the subject's referring/managing physicians will not be proactively informed of a subject's treatment assignment to minimize potential bias in the subject's care decisions. However, to specifically minimize potential bias in the measurement of Office BP and ABPM, each investigational site will specify several designated "blinded" members of their study staff that will not be informed of the subject's group assignments and will be responsible for performing the office blood pressure measurements, conducting ABPM preparation and printing results upon a patient completing the ABPM. Prior to unblinding, the blinding effectiveness will be assessed by asking blinded study staff which group they believe the subject was randomized to.

Subjects will be blinded during the renal angiogram by a combination of conscious sedation, sensory isolation (e.g., blindfold and music), and lack of familiarity to the procedural details and duration (i.e., subjects will not know the difference between the renal angiography procedure alone and the renal angiography and denervation procedure). Subjects will continue to be blinded by only interacting with blinded site personnel through the 6 month follow-up visit post-procedure. Blinding effectiveness will be assessed by asking the subject which group they believe they were randomized to. All subjects will be unblinded after the completion of their required 6-month follow-up testing.

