    - When possible, the subject should be referred to a local laboratory to collect samples. Laboratory Kits to be provided to subjects in advance of the visit by the study site.
  - Renal Artery Imaging:
    - Make every effort to scheduled in-person renal artery imaging as soon as possible.
    - When possible, subjects may be referred to a local imaging center for assessment. Local imaging technicians would require study training and delegation prior to assessment.
  - Office Blood Pressure and ABPM measurements may be collected and designated as subject-reported in the case report form.
    - Office blood pressure and ABPM units to be provided to the subjects in advance of the visit by the study site.
  - Witnessed pill intake prior to ABPM.
    - Documentation of pill intake will be assessed virtually.
- Phone Visit, i.e. no video with the subject. The following assessments may not be completed with a phone visit:
  - Clinical Assessment, limited review to be completed per physician discretion.
  - Laboratory Tests:
    - When possible, the subject should be referred to a local laboratory to collect samples. Kits to be provided to subjects in advance of the visit by study site.
  - Renal Artery Imaging:
    - Make every effort to schedule in-person renal artery imaging as soon as possible.
    - When possible, the subjects could be referred to a local imaging center for assessment. Local imaging technicians would require study training and delegation prior to assessment.
  - Office Blood Pressure and ABPM measurements may be collected and designated as subject-reported in the case report form.
    - Office blood pressure and ABPM units to be provided to the subjects in advance of the visit by study site.
  - Witnessed pill intake prior to ABPM.

- Documentation of pill intake will be assessed over the phone as confirmed verbally by subject.

In case the Symplicity Spyral™ catheter and Symplicity G3™ generator receive commercial approval in the United States, Canada and/or Japan during the course of this clinical study, the follow-up assessments will continue to be conducted as planned unless otherwise instructed.

Follow-up procedures for all subjects are listed below. Follow-up procedures must be performed by blinded site personnel through 6 months follow-up for each subject.

- a) **EQ-5D:** The Euro-Qol 5D (EQ-5D) will be administered at the 3, 6, 12, 24 and 36 month post-procedure visits to measure health outcomes.

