- i) **24-hour Ambulatory Blood Pressure Monitoring** will be conducted at each visit from the 3 month to the 36 month follow-up visits post-procedure according to the guidelines in Appendix L.7. A repeat ABPM will be required in the event of technical issues, failure to follow ABPM guidelines or if the minimum required number of daytime and nighttime readings is not obtained. If ABPM is repeated office blood pressure and drug testing must be repeated on day the ABPM is applied ().
- j) **Blinding Assessment** will be requested from all study subjects and study staff assessing BP at the 3- and 6-month follow-up visits to assess validity of the study blinding.
- k) **Mortality Assessment** will be completed by the investigational site when a subject cannot be reached after each of the protocol required follow-up visits..

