## 2. AMBULATORY BLOOD PRESSURE MONITORING

All 24 Hour Ambulatory Blood Pressure Monitoring (ABPM) measurements must be taken with the 24-hour ABPM device provided by the sponsor to ensure consistency.

Cuff size identified at SV2 should be used for the duration of the study.

- (1) If the subject is on antihypertensive medications, the visit should begin before 10:30am unless the subject normally takes their antihypertensive medication in the afternoon in which the subject's visit can occur in the afternoon.
- (2) Study personnel should observe the subject swallowing the antihypertensive medication(s), if applicable. Once this is completed and documented, the ABPM device should be applied to the subject and the recording started before leaving the office.
- (3) Place cuff on the subject's non-dominant arm.
- (4) Instruct the subject in proper cuff positioning in case they must remove it but stress the importance of leaving the BP cuff on.
- (5) The ABPM has pre-set parameters and should not be adjusted. These parameters are set to record blood pressure every 30 minutes.
- (6) Instruct subjects that they should engage in their usual physical level but should avoid strenuous exercise during the monitoring period
- (7) Instruct the subject to hold the arm still by the side while the device is taking a reading
- (8) Upon the return of the ABPM machine:
  - Submit the 24 Hour ABPM data to Medtronic
  - A 24 Hour ABPM will be considered adequate if the number of successful daytime readings captured is  $\geq 21$  and the number of successful nighttime readings captured is  $\geq 12$ . At SV2, a single repeat ABPM will be allowed in case of the following:
    - If the 24-hr systolic ABPM measured is between 135 and <140 mmHg or 170-175 mmHg
    - If a valid number of readings is not obtained
    - If there is a technical issue with the blood pressure monitor or failure to follow ABPM instructions.In all other instances at SV2, the ABPM will not be allowed to be repeated and the subject will be considered a screen failure

For all other time points with ABPM, make all efforts to obtain repeat ABPM from subject until the minimum number of readings is obtained.

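### Protocol G.3.4 allows unblinding during the 6-month visit, before the 24-hour ABPM started there is finished, while C.5 and SAP section 7 place it after the 6-month testing

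*Protocol*

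**What the plan says.** The time of unblinding is given in several places.

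- Protocol G.3.4, the section on criteria for unblinding: "All randomized patients will be unblinded during the 6 month follow-up visit".
- Protocol C.5, the section on randomization and blinding: "All subjects will be unblinded after the completion of their required 6-month follow-up testing". SAP section 7 repeats this sentence.
- Protocol synopsis, under Treatment: "Subjects and blinded study personnel will be unblinded to the randomization assignment at 6 months".

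Three further provisions bear on it. F.7 requires that "Follow-up procedures must be performed by blinded site personnel through 6 months follow-up for each subject". F.7 also asks for a blinding assessment, which "will be requested from all study subjects and study staff assessing BP at the 3- and 6-month follow-up visits". F.10 describes control subjects who take up crossover at the 6-month visit itself, and gives 30 days from the crossover visit for the procedure.

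**The concern.** G.3.4 and C.5 give different orders of events, and G.3.4 is where a site would look for the unblinding rule. If the allocation is revealed while the subject is still at the clinic, the ambulatory recording that has just begun, or is about to begin, is made by a subject who knows which procedure was done. A subject who learns that it was the sham may behave differently over the next day, or handle later doses differently.

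Six months is the last point at which the SAP compares RDN with an intact control group (SAP 9.9.8). After that, controls are split into crossover and non-crossover groups. C.5, F.7 and SAP section 7 all commit to blinding through this visit, so losing it for part of the 6-month data would be avoidable.

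**Working it through.** No sample size, power or error rate enters this point. The check sets the provisions side by side and follows the order of events.

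1. **Is ABPM part of the 6-month testing?** Yes. F.7 says that it "will be conducted at each visit from the 3 month to the 36 month follow-up visits post-procedure", and the testing schedule in Protocol Table 1 includes it at 6 months.

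2. **When does the recording run?** Appendix L.7 says that "the ABPM device should be applied to the subject and the recording started before leaving the office". It also sets readings every 30 minutes, so a full recording has 24 hours × 2 per hour = 48 scheduled readings. Only those taken before the subject leaves fall within the in-office part of the visit. The recording ends about a day later.

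3. **Can it run later still?** Yes. F.7 says "A repeat ABPM will be required in the event of technical issues, failure to follow ABPM guidelines", and adds too few daytime or night-time readings as a further reason. Office BP and drug testing must then be repeated on the day the device is re-applied. The synopsis unblinds the blinded staff as well as the subject. After unblinding on the visit day, a repeat could therefore produce both an ABPM and an office BP with neither subject nor assessor blinded, against the F.7 requirement for blinded personnel.

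4. **What order does each provision give?**
   - G.3.4: visit begins, ABPM is started, unblinding is allowed during the visit, and the rest of the recording is unblinded.
   - C.5 and SAP section 7: visit, ABPM and any repeat completed, then unblinding.
   - Synopsis: fits either order.
   - F.10: a control who accepts crossover at the visit must already know the allocation, which fits G.3.4 better than C.5.

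5. **Which analyses use the exposed data?** SAP 9.9.8 compares RDN with control up to 6 months, before crossover. The primary endpoint (24-hour SBP) and the powered secondary endpoint (office SBP) are both at 3 months, before any planned unblinding.

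**The case against.** The strongest reply is that G.3.4 does not mention ABPM and sets no order within the visit. The protocol often uses the word visit broadly. It defines completion of Screening Visit 2 by completion of the ABPM or laboratory results (F.5). F.9 speaks of completing a valid ABPM at the 3-month visit. F.10 treats the crossover baseline procedures, ABPM among them, as able to take place during a follow-up visit. If the 6-month visit lasts until the ABPM is complete, G.3.4 can be read together with C.5. C.5 is also the section to which C.4 and F.6 refer for blinding, and it gives an explicit order.

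This has weight: the two provisions can be reconciled, and G.3.4 does not require early unblinding. But no such definition is given for the 6-month visit. Even on the broad reading, a rule that allows unblinding during the visit still allows it before the recording or its repeat is finished.

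The rest of the reply stands and limits the point:

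- **Blinding assessment.** C.5 already places the staff assessment before unblinding. Asking subjects which group they believe they were in presupposes that they do not yet know.
- **Medication.** Antihypertensive intake is witnessed before the ABPM starts, and drug-test samples are taken at the visit. Only later doses during the recording could change.
- **Measurement.** ABPM is automated with fixed settings, so assessor influence is small.
- **Timing.** Section B.1.2 gives enrollment to October 2019 for the reported cohort and a stop in February 2020. Many 6-month visits may therefore precede this protocol version. That is an inference, because the version date is not visible in the text reviewed.

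**Conclusion.** The inconsistency is real and should be corrected. As worded, G.3.4 permits unblinding before the 6-month ABPM, or a repeat ABPM with its office BP, is finished; C.5 and SAP section 7 do not. What is exposed is the unpowered 6-month secondary BP comparison, chiefly 24-hour ABPM. Office BP taken at the visit itself is exposed only if unblinding comes first. This rests on the ordinary meaning of a visit and on some sites following G.3.4 rather than C.5. The documents do not show how many did, and give nothing from which to estimate the bias.

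Three stronger conclusions that a reader might draw are not supported:

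- The primary efficacy result is not compromised. Both powered efficacy endpoints are measured at 3 months.
- The 6-month medication-burden comparison (SAP 9.9.10) is not plausibly affected. It scores the class, dose and frequency of the drugs being taken at 6 months, a regimen built up since month 3 rather than by what the subject learns at the visit.
- The synopsis does not contradict C.5. It is only imprecise.

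**What to change.** Amend G.3.4 to match C.5 and SAP section 7. Where the schedule requires these tests, unblinding follows the 6-month office BP, the subject and staff blinding assessments, and a valid ABPM including any repeat. Add the following:

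- State that the 6-month duplex ultrasound is exempt from this condition. F.7 and F.10 waive it for controls who cross over within 30 days, and those controls cannot be identified until they are unblinded.
- Say what applies if no valid ABPM can be obtained, so that unblinding is not left open.
- Replace the synopsis wording with the same order.
- Reconcile F.10's account of crossover being accepted at the 6-month visit with that order.

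The cost is a few sentences and a crossover discussion that waits about a day, or longer when the ABPM is repeated, within a 30-day window.

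For visits already completed, G.3.4 requires the unblinding date to be documented. Compare it with the ABPM dates, report how many 6-month recordings ended after unblinding, and repeat the 6-month ABPM comparison without them as a sensitivity analysis. G.3.4 asks for a date and not a time, so recordings that ended on the unblinding date should be shown separately. The check uses records that the plan already requires.

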## G.4 Study close out

Upon study completion or termination Site Closeout Visits will be conducted, as outlined in the Monitoring Plan. After the study has been completed or terminated, medical care will be provided to the subjects upon the discretion of the treating physician.

In Japan, upon completion of the clinical study (when enrollment of all prospective subjects has been completed, all follow-up visits have been completed and data queries resolved and all eCRFs have been approved), the investigator will notify the institution director of the site closeout. Medtronic Japan will submit a clinical study notification to the regulatory authority at the time of study close-out.

## H DATA ANALYSIS AND REPORTING

Any deviations from this section and/or the Statistical Analysis Plan will be described and justified in the Final Clinical Study Report, as appropriate or justified in the CIP, if applicable.

### H.1 Analysis of clinical data

#### General Analysis Overview

Descriptive statistics of continuous outcomes will be presented by treatment arm and include sample size, mean, median, standard deviation, minimum and maximum. For categorical outcomes, the number and percentage of subjects in each category will be presented by treatment arm. Statistical comparisons between treatment arms will be made using t-tests for continuous outcomes and chi-square or Fisher's exact test (depending on overall event rates) for categorical outcomes. Paired t-tests will be used to compare changes from baseline to follow-up within each treatment arm. All statistical analyses will be performed using SAS for Windows (version 8.2 or higher) or other widely accepted statistical or graphical software. Patient data listings and tabular and graphical presentations of results will be provided. Unless otherwise specified, a two-sided 0.05 level of significance will be used to declare treatment arms significantly different. Additional details on the analysis will be provided separately in the SPYRAL HTN OFF-MED Statistical Analysis Plan (SAP) for this study.

#### H.1.1 Analysis Sets

- a. Intent-to-Treat (ITT): All randomized subjects, analyzed according to their randomized treatment. Subjects who meet the antihypertensive medication escape criteria (OSBP>180 or safety reasons) will be analyzed using Last Observation Carried Forward (LOCF) for their blood pressure measurements.
- b. Modified Intent-to-Treat : All randomized subjects, analyzed according to their randomized treatment. Subjects who meet the antihypertensive medication escape criteria (OSBP>180 or safety reasons) will be excluded from this population.
- c. Per-Protocol (PP): All randomized subjects, meeting the following criteria:
  1. Subjects showing medication compliance in blood and/or urine (via drug testing data) at SV2 and 3M

2. Exclude subjects with protocol deviation code 101 (consent not obtained)
  3. Exclude subjects who do not meet the following Inclusion/Exclusion criteria
    - Inclusion: Individual has an office systolic blood pressure (SBP)  $\geq$  150 mm Hg and  $<$ 180 mm Hg and an office DBP  $\geq$  90 mm Hg measured at Screening Visit 2, according to the guidelines in Appendix L7.
    - Inclusion: Individual has a 24-hour ABPM average SBP  $\geq$ 140 and  $<$  170 mm Hg measured at Screening Visit 2, according to guidelines in Appendix L7.
    - Exclusion: Individual has undergone prior renal denervation
    - Exclusion: Individual has renal artery anatomy that is ineligible for treatment
    - Exclusion: Individual has one or more of the following conditions: stable or unstable angina within 3 months of enrollment, myocardial infarction within 3 months of enrollment; heart failure cerebrovascular accident or transient ischemic attack or atrial fibrillation at any time.
  4. Exclude subjects meeting the antihypertensive medication escape criteria (OSBP $>$ 180 or safety reasons).
  5. Exclude subjects who did not receive the treatment they were randomized to.
- d. As Treated Population: All randomized subjects, analyzed according to the actual treatment received. Subjects randomized to RDN who do not get treated will be analyzed in the control arm. Subjects who meet the anti-hypertensive medication escape criteria will be analyzed using Last Observation Carried Forward (LOCF) for their blood pressure measurements out to 3 months.

## H.2 Primary Safety Objective

Medtronic is using a performance goal approach to analyze the primary safety endpoint. The safety performance goal for the Major Adverse Event (MAE) rate was developed based on review of and comparison to event rates of other renal interventions. The reported events differed among the studies; however, for a subset of these studies, we could estimate rates for a composite of events similar to our protocol's MAE composite. The major adverse event rate from these studies was 7.1% which will be used as the performance goal for the primary safety endpoint. Additional details on the performance goal calculation can be found in the SAP.

The primary safety null and alternative hypotheses are:

---

